Risks of DCS/Optical Blood Flow Monitoring: There is a risk of damage to the eye if the eye is exposed directly to the infrared light coming from the DCS patches. Damage could include retinal (light sensitive tissue at the back of the eye) burn. In order to prevent such an injury we will put optical fibers in a foam pad where they will be away from the surface of the skin. Therefore the light will be concentrated on the top of the head. The probes will be secured by a lightly wrapped bandage which will ensure that the light pads remain secure, covered, and away from the eyes. In addition the patient can elect to wear safety goggles that will reduce the risk of retinal damage if probes and protective foam become dislodged.

A research staff member will be continuously monitoring the subject while on the study and will be able to cycle the light off in less than three seconds. The instrument has passed clinical engineering safety inspection.

A member of the study team will be present at all times and will assist in the placement of the probe(s) and the collection of the data. No discomfort should be associated with the procedure.

Risks of Transcranial Doppler Monitoring:

There is no known risk of the use of ultrasound equipment for transcranial doppler monitoring. It is non-ionizing radiation, and therefore does not have the same risk as x-rays or other types of radiation.

A member of the study team will be present at all times and will assist in the placement of the probe(s) and the collection of the data. At times the TCD probes can cause mild discomfort. If the subject feels uncomfortable study personnel will attempt to reposition the probes to maximize comfort. If at any point the discomfort becomes significant, the study will be terminated.

Risks of non-invasive blood pressure monitoring:

There is no known risk of the use of non-invasive blood pressure monitoring via the Finapress system.

A member of the study team will be present at all times and will assist in the placement of the probe and the collection of the data. No discomfort should be associated with the procedure.

Risks of Thigh Cuff Manipulation of Blood pressure

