There is a risk of discomfort during the thigh cuff inflation. This discomfort will be related to the inflation of the cuff around the thigh and is expected to be the same amount of discomfort as experienced during routine brachial blood pressure measurement, only sustained for 3 minutes. A member of the study team will be present at all times. If the subject feels uncomfortable study personnel will attempt to reposition the cuffs around the thigh. If at any point the discomfort becomes significant, the study will be terminated.

2. Potential Study Benefits

There will be no direct benefit to subjects as a result of their participation in this study; however, information gained from this research will lead to a better understanding of cerebrovascular physiology.

3. Alternatives to Participation

Participation in this research study is voluntary. Subjects who do not wish to participate in the study will not be coerced into participating.

4. Data and Safety Monitoring

Who will monitor this study? Check all that apply.

- Principal Investigator
- \boxtimes Sponsor or contract research organization
- □ NCI sponsored cooperative group
- Cancer Center (if mandated by CTSMRC)
- Medical monitor
- Safety monitoring committee
- Data and safety monitoring board

5. Management of Information for Multi-center Research where a Penn Investigator is the Lead Investigator of a multi- center study, or Penn is the lead site in a multi-site study. Not applicable

6. Risk/Benefit Assessment

Low Risk: This study represents a minor increase over minimal risk. There is a small risk in retinal damage from infrared laser radiation from the optical blood flow monitor; however, the exposure of infrared light to the patient's eye is minimal to zero. Information gained from this study may be foundational for future use of DCS technology and ultimately help take care of patients with many types of brain injury. In light of the anticipated benefits to others, the risks, which are quite modest, are reasonable.

SUBJECT COMPENSATION

Subjects will be compensated with \$25.

INFORMED CONSENT

1. Consent Process

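### Goggles that the protocol says lower the risk of retinal damage if a probe comes loose are left to the subject's choice; making them the default is a cheap safety improvement

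*Combined protocol and SAP*

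**What the plan says.** Under Risk/Benefit Assessment, 1. Potential Study Risks, the protocol states the hazard: "There is a risk of damage to the eye if the eye is exposed directly to the infrared light coming from the DCS patches". Retinal burn is given as an example. The same paragraph describes fibers housed in foam and then the fixation: "The probes will be secured by a lightly wrapped bandage which will ensure that the light pads remain secure, covered, and away from the eyes". Goggles come last, as a back-up for one failure, namely that probes and foam come loose: "the patient can elect to wear safety goggles that will reduce the risk of retinal damage" in that event. The next paragraph says that a staff member watches the subject throughout and "will be able to cycle the light off in less than three seconds", and that the instrument has passed an engineering safety inspection.

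Item 6 of the same part gives the overall rating. The one specific risk it names is this: "There is a small risk in retinal damage from infrared laser radiation from the optical blood flow monitor". It adds that "the exposure of infrared light to the patient's eye is minimal to zero".

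Further safeguards stand elsewhere. The Background subsection on optical measurement describes black padding over each probe to contain the laser light, with adhesive tape and a Velcro band to hold it. Study Procedures, 1. Procedures repeats the tape and Velcro. Drugs or Devices reports that the university's radiation safety department has approved the instrument for laser safety.

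**The concern.** The protocol itself foresees that a pad may come loose and says that goggles would lower the risk in that event, yet it leaves their use to each subject. The subjects are healthy, receive no direct benefit, and number at most 30 (Characteristics of the Study Population, 2. Accrual). Retinal burn is the most serious injury that the risk section names. A safeguard already on offer could be made routine at little cost.

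Two gaps in the text bear on the same point. The source is not tied to the handling of the pads: nothing says that it comes on only after fixation or goes off before adjustment and removal. And the protocol describes probe location and fixation in two different ways, although the statement that eye exposure is negligible relies on both.

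**Working it through.** The plan states no figure that could be reproduced here, so the check is mainly a comparison of passages.

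**Step 1. Which stated safeguards still act once a pad is loose?**

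| Safeguard | Where stated | Once a pad is loose |
|---|---|---|
| Foam housing, bandage | Potential Study Risks | Failed, by the scenario |
| Tape and Velcro | Background (optics); Procedures | Failed, by the scenario |
| Black padding on the probe | Background (optics) | Not stated whether it still contains the light |
| Laser-safety approval; engineering inspection | Drugs or Devices; Potential Study Risks | Concern the instrument; not stated whether a loose pad was considered |
| Staff cut-off | Potential Study Risks | Acts |
| Goggles | Potential Study Risks | Act, if worn |

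For a subject without goggles, one active safeguard remains: the staff cut-off. The text gives it as a capability of under three seconds and does not say from what moment the time runs.

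**Step 2. Location and fixation.**

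| | Potential Study Risks | Background (optics) and Procedures |
|---|---|---|
| Where the light is | On top of the head | Frontal regions; outer edge of the forehead |
| What holds the probes | Light bandage | Adhesive tape and a Velcro band or strap |

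The safety argument rests on distance from the eyes and on secure fixation. The document gives two versions of each.

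**Step 3. When are pads or nearby equipment handled?** Procedures places the Doppler probes at the temporal bone in a head frame, close to the optical pads. Potential Study Risks allows the Doppler probes to be moved if they are uncomfortable. Study Design, 3. Study Duration allots about half an hour to setup and removal. None of these sections says whether the source is on or off at those times.

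**Step 4. Can the exposure be sized?** Only total emission can be computed, from the stated average input power of 15 mW (Background, optics):

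energy emitted = average power × time to cut-off

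- 15 mW × 0.5 s = 7.5 mJ
- 15 mW × 1 s = 15 mJ
- 15 mW × 2 s = 30 mJ
- 15 mW × 3 s = 45 mJ (a bound, since the stated time is less than three seconds)

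This is light leaving the source. It is not a retinal dose. The text does not say whether 15 mW is per probe or in total, and it gives no beam geometry, exposure limit or probability of dislodgement. The figures therefore show neither harm nor safety.

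**The case against.** The strongest reply is that nothing here is wrong. The hazard is disclosed, several layers of prevention are described, and goggles are offered on top of them. Optional goggles conflict with no other passage. The instrument has institutional laser-safety approval, whose content is not in these documents and which may have dealt with a loose pad. This is an IRB summary, so rules for switching the source may stand in an operating procedure. Goggles are also not free of side effects: they would share space with the forehead pads, the strap and the head frame, and the bibliography lists a paper on how probe pressure influences the optical flow signal.

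Most of this stands, and it limits the point to an improvement. It does not remove the observation that, in the one failure the protocol names, a subject without goggles depends on staff reaction alone. Nor does it explain the two accounts of location and fixation.

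A reader might infer more than the documents support:

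- **That the bandage is the only physical barrier.** It is not; black padding, tape and Velcro are also described.
- **That thigh-cuff inflation or release could shift a forehead pad.** No passage links the two. The cuffs are on the thighs of a supine subject. Handling of the Doppler probes or head frame is the more plausible route, though it too is an inference.
- **That 45 mJ measures the danger to the eye.** It does not, for the reasons given in step 4 of the working.
- **That subjects who decline goggles should not be studied.** That would add an eligibility rule for which the documents give no basis.

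**Conclusion.** This is a cheap improvement in subject safety. It is not an error and has no bearing on the sample size or the analysis. The documents establish three things: goggles are said to lower the risk if a pad comes loose, wearing them is optional, and staff cut-off is then the only active safeguard named for a subject without them. The documents do not establish that the present controls are inadequate. The size of the residual risk is unknown. The conclusion assumes that the approval and inspection did not already settle the question of a loose pad, and that no separate operating procedure governs the source.

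The two descriptions of location and fixation are a genuine inconsistency. Until they are reconciled, the statement that eye exposure is negligible lacks a consistent basis in the text.

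**What to change.** 1. In Potential Study Risks, make the goggles already on offer the default whenever the source is on. Make this subject to agreement by the laser-safety reviewers and to a check that the goggles neither press on nor move the optical pads. Do not make acceptance a condition of taking part.
2. State that the source is turned on only after both pads are secured, and is off during adjustment or removal of the pads, Doppler probes or head frame.
3. Reconcile probe location and fixation between Potential Study Risks, the optics part of the Background and Procedures. Then confirm that the exposure statement in the overall assessment still follows.

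The cost is a few sentences of protocol text, a short fitting check and the reviewers' agreement. The downsides are slight discomfort, fitting around the pads and head frame, and possible pressure on the probes.

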Non-Invasive Measurement of Dynamic Autoregulation of Cerebral Blood Flow Using Diffuse Correlation Spectroscopy

Principal Investigator:	[name], MSCE [name] [contact]
	[contact]
IRB Number:	821705
NCT number:	NCT02442856
Date:	March 17, 2016

Application for Review of Human Research: IRB Protocol Summary Biomedical Research

Section II

Principal Investigator: [name], MSCE [name] [contact]

PROTOCOL # 821705

Date: March 17, 2016

PROTOCOL TITLE

1. *Full Title:* Non-Invasive Measurement of Dynamic Autoregulation of Cerebral Blood Flow Using Diffuse Correlation Spectroscopy

2. Brief Title: Non-invasive Measurement of Cerebral Dynamic Autoregulation

STUDY SPONSORSHIP

1. Funding Sponsor: NIH R25 Research Grant

PROTOCOL ABSTRACT

List of Abbreviations

OBJECTIVES

1. Overall Objectives

The overall objective of this study is to evaluate the use of diffuse correlation spectroscopy (DCS) to non-invasively measure dynamic cerebral autoregulation (dCA). Cerebral autoregulation (CA) refers to the process by which cerebral blood vessels change their caliber to ensure constant cerebral blood flow (CBF) in the face of changes in cerebral perfusion pressure (CPP). Optical cerebral blood flow (oCBF) measurements will be correlated with changes in arterial blood pressure (ABP) to assess how CBF is maintained in response to changes in ABP. CA measured by DCS will be compared with reference measurements using Transcranial Doppler (TCD).

2. Primary Objective

The primary objective of this study is to validate the use of DCS to quantify dCA in healthy controls. We will measure dCA with both TCD and DCS during acute changes in mean arterial pressure using thigh cuff deflation techniques in healthy subjects. Measurements will be compared between TCD and DCS in order to validate DCS as a tool to measure dCA. We hypothesize that DCS based measurements will be tightly correlated to TCD based measurements. We hypothesize that continuous oCBF measurements will allow calculation of an autoregulation index that will correlate well with established methods for measuring CA using TCD. The primary measured variable will be relative change in cerebral blood flow using DCS.

BACKGROUND

Cerebral Autoregulation

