After obtaining informed consent, all subjects will be placed supine with the head of bed flat. A non-invasive Finapres blood pressure probe will be placed on a finger to continuously record arterial blood pressure. Heart rate will be calculated by analyzing the frequency of pulsatile blood flow. After the patient is comfortable optical probes will be attached to the patient's forehead. The probes are embedded in foam pads that will be secured to each side of the forehead using a combination of medical adhesive tape and a padded Velcro strap. The pads will be placed at the temporal margin of the forehead, superior to the frontal sinuses. A transcranial Doppler ultrasound probe will be placed on the scalp at the temporal bone to insonate the middle cerebral artery (MCA) and/or the anterior cerebral artery (ACA) bilaterally and secured in place using a commercial head frame The goal will be to insonate the MCA on one side and the ACA in the contralateral side. Due to limitations of TCD insonation and variability in temporal bone windows, this may not be possible in all subjects. In this way, optical blood flow from the right and left frontal cortex and blood flow velocity in the anterior cerebral circulation will be recorded simultaneously during the study session. A large blood pressure cuff will be placed around each thigh. Both cuffs will be connected together with a large bore Y-adapter that is connected to a bulb inflator.

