Once the patient is comfortable, optical blood flow and TCD blood flow velocity will be measured for 5 minutes to establish a baseline. Both thigh cuffs will then be inflated to 20 mmHg above the patient's systolic blood pressure so that blood flow to the legs is occluded. Occlusion will be maintained for 4 minutes, followed by simultaneous deflation of bilateral cuffs and concurrent recording of blood pressure and CBF for an additional 4 minutes; 3 measures will be obtained per subject and averaged to establish a curve. The rapid deflation of the thigh cuffs will induce a 5-10% step decrease in blood pressure that is expected to last for about 10 seconds before cardiovascular reflexes restore MAP to baseline levels. During the thigh cuff deflation, changes in pulsatile blood pressure, and TCD blood flow velocity will be continuously recorded; oCBF will be recorded every 0.5 seconds. Intact autoregulation should cause a restoration of cerebral blood flow to pre-deflation values within 5-10 seconds in spite of the prolonged decrease in systemic blood pressure. We expect to see a sudden drop in optical cerebral blood flow and MCA velocity followed by a quick increase in both of these parameters. The change in cerebrovascular resistance (Δ CVR) can be calculated by dividing arterial blood pressure by cerebral blood flow. Δ CVR will be calculated using both optical CBF values and MCA velocity. The magnitude of Δ CVR over time gives a measure of dynamic cerebral autoregulation (see below for details regarding analysis). The thigh cuff occlusion will be repeated 4 times in each subject to establish a curve. A diagram of the study flow is shown below:

2. Data Collected

Information will be collected and stored securely from all study subjects. This information will include the following: age, sex, past medical history, current medications, non-prescription drug use.

3. Quantitative and Statistical Analysis

dCA will be calculated as change in blood pressure from baseline (Δ BP) divided by change in cerebral blood flow from baseline (Δ CBF) at each time point, thus dCA = Δ BP/ Δ CBF(Aaslid, Lindegaard et al. 1989); this data will be plotted against time in seconds.

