The data recorded from the TCD monitoring will be used to quantify the relation between changes in cerebrovascular resistance (Δ CVR) and blood pressure (Δ BP) as calculated by ROR = (Δ CVR/ Δ T)/ Δ BP and will be plotted along a curve for the first few seconds after cuff deflation (Aaslid, Lindegaard et al. 1989, Tiecks, Lam et al. 1995, Panerai, White et al. 1998, Lang, Mehdorn et al. 2002). The purpose of collecting TCD data is to show a correlation between the ROR calculated from TCD measures to that of dCA via DCS measurement, further validating our DCS measurements.

The optical CBF output is directly recorded as relative CBF. For blood flow velocity measured by TCD, relative CBF can be approximated by normalizing flow to baseline. This is an approximation of CBF that assumes that the vessel diameter does not change over time. Once the relative change in CVR over time is calculated, a dynamic rate of regulation index (dRoR) can be calculated by dividing the slope of the CVR over time curve by the maximum change in blood pressure (i.e. (Δ CVR/ Δ t)/ Δ BP). Intuitively, if autoregulation is intact, there should be a steep decrease in cerebrovascular resistance with a drop in blood pressure. Perfect autoregulation would result in dRoR = 1.

Baseline heart rate, MAP, and MCA velocity will be recorded for each subject and descriptive statistics including mean and standard deviation will be reported for these values. For dRoR calculation, a mean dRoR will be calculated for each subject (from 5 trials) using both optical CBF and TCD. The optical dRoR and TCD dRoR will be compared for each subject and significant differences will be evaluated using Student's t-test or Wilcoxon rank-sum as appropriate. We will quantify the correlation between dRoR measured with TCD and DCS using Pearson or Spearman correlation coefficient as appropriate.

4. Confidentiality

How will confidentiality of data be maintained? Check all that apply.

- Paper-based records will be kept in a secure location and only be accessible to personnel involved in the study.
- Computer-based files will only be made available to personnel involved in the study through the use of access privileges and passwords.
- Prior to access to any study-related information, personnel will be required to sign statements agreeing to protect the security and confidentiality of identifiable information.
- Whenever feasible, identifiers will be removed from study-related information.

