 - Specific, relevant criteria not otherwise captured (e.g. time frames of screening tests that are not apparent in records)

2. Waiver of Authorization

Not applicable

RESOURCES NECESSARY FOR HUMAN RESEARCH PROTECTION

All research staff have completed their Patient Oriented Research Training (POR) and/or Collaborative Institutional Training Initiative (CITI). There will be study-specific "Team Meetings" to train and review study processes ensuring compliance, patient safety and confidentiality. Study-specific monitoring will be conducted by the study sponsor as well UPHS regulatory committees responsible for review of patient oriented research.

Neither [name] nor [name] will consent study subjects. [name] and [name] will not personally acquire the primary data nor personally calculate the results of the primary data. In those cases where TCD data may be generated, to the extent (if any) [name] oversees analysis of any TCD data, he will do so without knowledge of the optical device findings.

Bibliography

Aaslid, R., K. F. Lindegaard, W. Sorteberg and H. Nornes (1989). "Cerebral autoregulation dynamics in humans." Stroke **20**(1): 45-52.

Adams, H. P., Jr., G. del Zoppo, M. J. Alberts, D. L. Bhatt, L. Brass, A. Furlan, R. L. Grubb, R. T. Higashida, E. C. Jauch, C. Kidwell, P. D. Lyden, L. B. Morgenstern, A. I. Qureshi, R. H. Rosenwasser, P. A. Scott and E. F. Wijdicks (2007). "Guidelines for the early management of adults with ischemic stroke: a guideline from the American Heart Association/American Stroke Association Stroke Council, Clinical Cardiology Council, Cardiovascular Radiology and Intervention Council, and the Atherosclerotic Peripheral Vascular Disease and Quality of Care Outcomes in Research Interdisciplinary Working Groups: The American Academy of Neurology affirms the value of this guideline as an educational tool for neurologists." Circulation **115**(20): e478-534.

Aoi, M. C., K. Hu, M. T. Lo, M. Selim, M. S. Olufsen and V. Novak (2012). "Impaired cerebral autoregulation is associated with brain atrophy and worse functional status in chronic ischemic stroke." PLoS One **7**(10): e46794.

Arciero, R. A., C. R. Scoville, R. A. Hayda and R. J. Snyder (1996). "The effect of tourniquet use in anterior cruciate ligament reconstruction. A prospective, randomized study." Am J Sports Med **24**(6): 758-764.

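### The masking rule covers one overseer of TCD analysis only; nothing keeps the TCD result from whoever derives the DCS index, and the slope fit is left open for both devices

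*Combined protocol and SAP*

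**What the plan says.** The masking text is in Resources Necessary for Human Research Protection. It opens with a condition, "In those cases where TCD data may be generated, to the extent (if any"), and then says of one person overseeing TCD analysis that "he will do so without knowledge of the optical device findings". The sentence before it separates roles: two named people "will not personally acquire the primary data nor personally calculate the results of the primary data". I found no other masking provision, no order in which the two devices are to be analysed, and no lock on either set of values.

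The quantity at issue is defined in Study Procedures, 3. Quantitative and Statistical Analysis. dRoR is obtained by "dividing the slope of the CVR over time curve by the maximum change in blood pressure". It is computed from both devices, averaged over several cuff releases per subject, and the two sets of subject means are then correlated. No start time, end time, filter or fitting method is given for either device. The one reference to timing, "will be plotted along a curve for the first few seconds after cuff deflation", belongs to the sentence on the TCD rate of regulation.

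Study Procedures, 1. Procedures says that the two signals "will be recorded simultaneously during the study session" and that "oCBF will be recorded every 0.5 seconds". Under Objectives, the aim is to validate DCS against TCD, and "The primary measured variable will be relative change in cerebral blood flow using DCS".

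**The concern.** In a method-comparison study the new method should be read without knowledge of the reference. Here the direction stated is the other one: an overseer of the reference method is masked to the new one. The DCS reading is the one being validated, and no masking protects it.

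This matters because the derivation leaves room for judgement. At one DCS value per 0.5 s, a window of 3 s, taken as an illustration, holds about 3 / 0.5 = 6 intervals. Moving either end by a second can therefore change the fitted slope. If such choices are made with the TCD value for the same subject in view, even in good faith, they will tend to favour the fit that agrees. A positive correlation can then appear with no true relation behind it, and the one-sided 5% error rate no longer holds.

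The point is about how each dRoR value is derived. Which subjects count as analyzable is a separate matter.

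**Working it through.** **1. The plan's own figure.** Inputs from Characteristics of the Study Population, 2. Accrual: n = 20, rho = 0.6, one-sided alpha = 0.05, Pearson correlation, stated power 90%.

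- Fisher z: power = Φ(atanh(0.6) × √17 − 1.645) = Φ(0.693 × 4.123 − 1.645) = Φ(1.213) = 88.7%.
- With the bias term 0.6 / (2 × 19) = 0.0158 added to 0.693: 89.9%.
- Simulation of bivariate normal data (400,000 sets): 90.4%.

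The stated 90% reproduces as a one-sided test; two-sided it would be 82% to 84%. The sample size is not in dispute. The test under study is therefore the one-sided Pearson test at n = 20. Its critical value is r = 1.734 / √(18 + 1.734²) = 0.378.

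**2. Model for an unmasked slope choice.** The documents do not give the number of plausible windows or how closely their results agree, so both are assumptions.

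- True correlation zero; TCD values standard normal.
- K candidate DCS values per subject, independent of TCD, with equal pairwise correlation c.
- K = 2 or 3; c = 0.9 or 0.7.
- 40,000 sets of 20 subjects per setting. The Monte Carlo standard error near 5% is √(0.05 × 0.95 / 40,000) = 0.1 percentage points.
- Selection acts once, on the subject's value. Selection release by release is not modelled.

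**3. False-positive rate (share of sets with r > 0.378).**

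| How the DCS window is settled | K=2, c=0.9 | K=2, c=0.7 | K=3, c=0.9 | K=3, c=0.7 |
|---|---|---|---|---|
| One common window for all subjects, chosen for best correlation with TCD | 7.0% | 8.1% | 7.9% | 10.4% |
| Every subject: keep the window nearest TCD | 13.9% | 26.7% | 21.4% | 48.0% |
| Mean spurious r in the row above | 0.11 | 0.22 | 0.18 | 0.35 |

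If only a quarter of subjects are tuned, the rate is 7% to 10% over the same settings (7.6% and 10.0% for K = 3). If half are tuned, it is 9% to 18%.

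**4. The masked comparator.** With 5 windows and one picked per subject without reference to TCD, the rate is 4.9% to 5.2% for c between 0.95 and 0.50, and mean r is about zero. This is expected: a choice that does not depend on TCD leaves the DCS value independent of TCD. In this model the inflation comes from knowing TCD, not from having several windows.

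**5. Sensitivity.** Widening the assumptions to K = 2 to 5 and c = 0.95 to 0.50 gives 7% to 17% for one common window and 11% to 92% when every subject is matched. The size depends heavily on inputs that the plan does not supply.

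**The case against.** Four things can be said for the plan.

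*There is a safeguard.* Two named people are kept from measuring and calculating. That stands as a separation of roles and bears on who could fit a slope. It does not answer the point, because it masks nobody who does the calculation.

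*The risk is inferred from silence.* A reader might infer that the DCS analyst will work with TCD results on screen, or will fit slopes by hand. The documents say neither. Simultaneous recording makes joint viewing easy but does not show that it will happen. This stands: the gap is that the plan does not prevent it.

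*Matching every subject is extreme.* Keeping the nearest window in all 20 subjects is deliberate matching, not ordinary unmasked fitting. This also stands, and the 14% to 48% range should be read only as an upper case. It is also tempting to justify low agreement between windows from the behaviour of slopes fitted to pure noise. That would not describe dRoR, which is a subject mean over several releases of a physiological response; any stable difference between subjects raises agreement between windows.

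*A fixed algorithm would do most of the work.* If window, filter and baseline were set in advance and applied identically, little discretion would remain even for an unmasked analyst. I agree, but no algorithm is specified. Manual overrides would still need masking.

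**Conclusion.** The point holds as a gap in protection and an inexpensive improvement. Masking is conditional, covers one person and runs in one direction, while the DCS dRoR that the study sets out to validate is derived by unmasked analysts from a slope with no fixed window or fitting method.

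The plausible size is a rise from 5% to about 7% to 10% if one common window is chosen, or a quarter of subjects are tuned, with TCD in view. The worst case is 14% to 48%. Both ranges assume zero true correlation, n = 20, the one-sided Pearson test, and 2 or 3 candidate windows correlated 0.9 to 0.7.

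A reader might go further and infer that the study's correlation will be an artefact, or that its error rate will be near one half. The documents do not support either: they do not describe unmasked fitting, and the highest figures need matching in every subject. Nor should the wording about the first few seconds be read as a loose window set for DCS. It is stated for TCD, and for DCS no window is stated at all.

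**What to change.** - Extend the existing masking rule to everyone who derives a dRoR, in both directions: DCS analysts without the TCD results, TCD analysts without the DCS results.
- Freeze one script for both devices, covering window, filter and baseline, before any subject's DCS and TCD dRoR values are viewed together.
- Run it on coded, device-separate files. Make any manual override on the coded file and log it.
- Lock both sets of dRoR values before merging them for the correlation.

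The cost is about a paragraph of protocol text and some file coding. The same analysts can do the work, and no subjects, measurements or staff are added. The downside is that a window that proves poor after the lock can be revisited only as a labelled sensitivity analysis.
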